### Figure 1 Study Schematic

For the purposes of this study, 'self-administration' is defined as either the administration of mepolizumab liquid drug product in autoinjector by the subject themselves or by their caregiver. If applicable, only one caregiver per subject will be permitted.

Subjects will receive 100 mg mepolizumab SC as a single injection that is selfadministered in the thigh, abdomen or administered in the upper arm (caregiver only), using the liquid drug product in autoinjector presentation. The site of administration will be recorded.

Subjects (and/or their caregiver, if applicable) will self-administer mepolizumab liquid drug product in autoinjector for the first time immediately after being trained in its use at Visit 2 (i.e. the Start of Study Visit). The training is designed to be representative of the instruction and training materials, including the Instructions for Use (IFU) that will be provided once the device is commercially available [Note: the autoinjector is referred to as a 'pre-filled pen' in the IFU]. Each autoinjector will have labelling that includes a pictogram plus standard labelling elements, or a standard labelling without the pictogram dependant on the country in which it is being used.

Three doses of mepolizumab liquid drug product in autoinjector will be self-administered by the subject/caregiver at 4-weekly intervals; 2 doses will be administered under observation in the clinic (at Visits 2 and 4). The second in clinic administration (Visit 4) will not include any onsite training or support, other than the IFU, which could assist the subject. One dose will be administered outside the clinic and without observation (within 24 hours after attending the clinic for Visit 3). Following each injection, subjects will complete a patient diary, included in the Study Reference Manual (SRM), and report the pain experienced immediately following, 1- and 24-hours post injection. Observations about the injection will be recorded by the investigator or designee for the doses administered in the clinic using an observer checklist. For the unobserved dose administered at home, a similar checklist detailing the steps required to successfully

administer the injection will be completed by the subject/caregiver. All injections will be assessed for success based on:

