- Direct observation of the self-administration using the Observer Checklist if the mepolizumab dose was administered in the clinic, and inspection of the autoinjector
- Subject/caregiver completed checklist and inspection of the returned autoinjector if the mepolizumab dose was administered outside the clinic

A self-administered injection is considered successful if the following criteria are met:

- Use of a correct injection site (abdomen/thigh or upper arm [caregiver only])
- Full dose administration: subject pushes the autoinjector all the way down and holds until either the second click, or the plunger stops moving and the inspection window is filled with the yellow indicator or pushes the autoinjector all the way down and holds for a total of 15 seconds
- No observations are made with respect to the autoinjector, following inspection, which indicates the full dose has not been dispensed

If the above criteria are met, the investigator or designee will confirm the injection was successfully delivered.

Any unsuccessful injection will undergo a root-cause investigation, following a scripted approach, and evaluation to assess whether the unsuccessful injection was associated with the instructions / use of the device or whether it was associated with a device failure using the Autoinjector (Pen) Error/Failure Reporting Form, further details of which can be found in the SRM. All devices will be evaluated by Device Engineering at GlaxoSmithKline (GSK), post-use, to assess overall performance and robustness of the device.

At the End of Study Visit, subjects will be asked to record their overall experience with the autoinjector including device performance.

In all subjects, blood samples for both PK, haematology assessment (which will include blood eosinophil count for the pharmacodynamic effect assessment) and clinical chemistry assessment will be collected at the time points indicated in the Time and Events Table (Section 7.1).

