## 6.8.2. Self-Administration Outside the Clinic

The subject (or caregiver) will self-administer the dose of study treatment outside the clinic and without observation during Week 4, up to 24 hours after attending clinic Visit 3. The subject/caregiver will complete a checklist of the steps required to use the autoinjector, which will also include the date and time of dose, site of injection, person administering the dose (subject/caregiver) and the ease with which the subject/caregiver was able to complete each of the critical steps required to administer the dose from the autoinjector. In addition, the subject will complete the patient diary capturing the pain experienced by the subject immediately following, 1- and 24-hours after the dose.

Subjects will be instructed to contact clinical study staff if they have concerns or questions regarding self-administration. They will have the option of returning to the clinical site for further training or assistance with self-administration. Requirement for additional training will be documented.

Compliance with the autoinjector will be assessed through reviewing the subject completed checklist, inspection of the returned autoinjector and querying the subject during the next site visit (Visit 4) and documented in the source documents.

For self-administration of mepolizumab outside of the clinic (at home), subjects should be instructed to call the investigator and/or go to an Emergency Department for any unusual symptoms (e.g. skin rash [hives] or redness, swelling of the face or mouth, becoming wheezy, coughing or having difficulty in breathing and/or feeling weak or light headed).

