#### 204959

## 7.1. Time and Events Table

		Pre-screening Week -6 to Week - 5ª	Screening Week -4 to Week - 1	Week 0 (Day 1)	Week 4 (±7 days)	Week 8 (±7 days)	Week 12 (±7 days)
		v					Early Withdrawal b
Procedures	Visit number	V0	V1	V2	V3	V4	V5
Informed consent		Х					
Demography/child bearing status asso	essment	Х					
Medical history			Х				
Asthma and Exacerbation history		Х					
Asthma Therapy history		Х					
Smoking history			Х				
Parasitic screening c			Х				
Prior needle use / self-administration	assessment		Х				
Inclusion/Exclusion criteria			Х				
Training session				Xď			
Autoinjector self-administration in clinic				Х		Х	
Autoinjector self-administration outsid	e of clinic				X e, f		
Laboratory:							
Urine pregnancy test			Х	Xď	Xď	Xď	Х
Hematology (including eosinophils) g /	Clinical Chemistry		Х	Xď	Xď	Xď	Xď
Urinalysis			Х				
Immunogenicity				Xď			Xď
PK				Xď	Xď	Xď	Xď
Pharmacogenetics h				Х			
Physical/Clinical:							
Vital signs i			Х	Xq	Xď	Xď	Х
12-lead ECG			Х				Х
Physical examination			Х				Х
Weight			Х				
Concomitant Medication		Х	Х	Х	Х	Х	Х
Asthma Exacerbations			Х	Х	Х	Х	Х
Serious Adverse Events j,k,l		Х	Х	Х	Х	Х	Х
Adverse Events j,k,l				Х	Х	Х	Х

	Pre-screening Week -6 to Week -	Screening Week -4 to Week -	Week 0 (Day 1)	Week 4 (±7 days)	Week 8 (±7 days)	Week 12 (±7 days)
	5	1	,			End of Study/ Early Withdrawal b
Procedures Visit number	VO	V1	V2	V3	V4	V5
Dispense patient diary			Xm	Х	Х	
Return/review patient diary				Х	Х	Xn
Dispense autoinjector for self-administration outside of clinic				Х		
Return/ inspect autoinjector following self-administration					Х	X n,o
outside of clinic						
Subject completed pain assessment diary (0, 1- and 24-			Х	Xf	Х	
hours post dose)						
Autoinjector observer assessment checklist			Х		Х	
Subject/caregiver completed autoinjector checklist				Xf		
Assessment of injection success			Х		Xp	
Device usability/functionality questionnaire						Х
Exit Interview Q						(X)

a. Pre-screening Visit can occur on the same day as the Screening Visit but must be completed prior to initiating any Visit 1 procedures; The Pre-screening Visit can be conducted up to a maximum of 2 weeks prior to the Screening Visit.

- b. The Early Withdrawal Visit will occur 4 weeks (±7 days) after last dose of mepolizumab for any subject who withdraws prior to Week 12

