- c. Parasitic screening is only required in countries with high-risk or for subjects who have visited high-risk countries in the past 6 months. Sites should use local laboratories.
- d. Perform prior to mepolizumab administration during the study and prior to restarting pre-study mepolizumab treatment on study completion/early withdrawal.
- e. Subjects will be instructed to contact clinical study staff at any time if they have concerns or questions regarding self-administration. They will have the option of returning to the clinical site for further training or assistance with self-administration. Requirement for additional training or assistance will be documented.
- f. Self-administration of mepolizumab using the autoinjector should occur within 24 hours following the clinic visit.
- g. Includes measurement of eosinophil levels for pharmacodynamic analysis at Visits 2, 3, 4 and 5
- h. Pharmacogenetic sample may be drawn any time after the respective informed consent form is signed and the subject is enrolled.
- i. Vital signs include temperature, sitting blood pressure, respiratory rate and pulse.
- j. Any SAEs assessed as related to study participation (e.g., study treatment, protocol-mandated procedures, invasive tests, or change in existing therapy) or related to a GSK concomitant medication, will be recorded from the time a subject consents to participate in the study up to and including any follow up contact. All other AEs/SAEs are recorded from the start of study treatment until the End of Study / Early Withdrawal visit.
- k. Injection site reactions (e.g., induration, erythema, edema, rash, pruritus, pain) are to be recorded on both AE and SAE CRF forms.
- I. Information on systemic reactions and events that meet the anaphylaxis criteria is collected on both AE and SAECRF forms
- m. Patient diary should be dispensed prior to administration of injection
- n. For any subject who withdraws prior to Week 12, patient diary and study drug for self-administration outside of clinic will be returned at the Early Withdrawal visit (if applicable).

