#### 2016N275054\_04

#### CONFIDENTIAL

204959

o. Assessment to be completed at the Early Withdrawal visit only if the dose of mepolizumab immediately prior to withdrawal was administered outside of the clinic.

- p. Includes both the injection outside the clinic from Week 4 and the injection in clinic at Week 8
- q. In a subset of subjects only. Completed over the telephone after the End of Study/Early Withdrawal Visit

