Subjects will complete a patient diary at Week 0, 4 and 8 recording the pain experienced immediately following, 1- and 24-hour after the injection (see SRM). At Week 4, when self-administration is performed outside the clinic (within 24-hours of attending the Visit 3 clinic visit), the subject/caregiver will also record the date and time of injection, site of injection, who administered the injection (subject or caregiver) and complete a checklist similar to the Observer Checklist outlining the various steps in the IFU and whether each step was completed easily, with some difficulty, or not completed (see SRM). The responses on the checklist will be checked by the Investigator or designee at the next clinic visit (Visit 4). Failure to perform one of the critical steps will deemed to be a failure to successfully administer the injection.

All devices utilised as part of the study will be returned to the clinic where they will be assessed to confirm that the device has been successfully actuated. Any unsuccessful injection will undergo a root-cause investigation, following a scripted approach, and evaluation to assess whether the unsuccessful injection was associated with the instructions / use of the device or whether it was associated with a device failure using the Autoinjector (Pen) Error/Failure Reporting Form, further details of which can be found in the SRM. All devices, will be evaluated by Device Engineering, post-use, to assess overall performance and robustness of the device.

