**CONFIDENTIAL**

204959

- j. Any SAEs assessed as related to study participation (e.g., study treatment, protocol-mandated procedures, invasive tests, or change in existing therapy) or related to a GSK concomitant medication, will be recorded from the time a subject consents to participate in the study up to and including any follow up contact. All other AEs/SAEs are recorded from the start of study treatment until the End of Study / Early Withdrawal visit.
- k. Injection site reactions (e.g., induration, erythema, edema, rash, pruritus, pain) are to be recorded on both AE and SAE CRF forms.
- l. Information on systemic reactions and events that meet the anaphylaxis criteria is collected on both AE and SAE CRF forms.
- m. Patient diary should be dispensed prior to administration of injection
- n. For any subject who withdraws prior to Week 12 (V5), patient diary and study drug for self-administration outside of clinic will be returned at the Early Withdrawal visit (if applicable).
- o. Assessment to be completed at the Early Withdrawal visit only if the dose of mepolizumab immediately prior to withdrawal was administered outside of the clinic.
- p. Includes both the injection outside the clinic from Week 4 (V3) and the injection in clinic at Week 8 (V4)
- q. In a subset of subjects only. Completed over the telephone after the End of Study/Early Withdrawal Visit

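### Could the Visit 4 questions about the home injection coach the subject before the observed Week 8 dose?

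*Protocol*

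**What the plan says.** Four sets of home-dose activities meet at Visit 4, the visit of the observed Week 8 injection.

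- **Compliance query.** Protocol Section 6.8.2 bases compliance with the home dose on the completed checklist, the returned pen and "querying the subject during the next site visit (Visit 4) and documented in the source documents".
- **Checklist and pen.** Section 7.3 has staff check the home checklist at Visit 4, and Section 6.6 has the used pen returned and inspected then. The Time and Events Table (Section 7.1) carries the matching row, "Return/ inspect autoinjector following self-administration" outside the clinic.
- **Success assessment.** Footnote p to that table says of the single Visit 4 entry: "Includes both the injection outside the clinic from Week 4 and the injection in clinic at Week 8". The SAP's copy of the table (Appendix 1) carries the same footnote and adds no order.
- **Root cause.** Section 4.1 states: "Any unsuccessful injection will undergo a root-cause investigation, following a scripted approach". Section 7.3 repeats this. Neither gives a visit for it.

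Two provisions bear on order and on help. Footnote d reads "Perform prior to mepolizumab administration during the study" and at Visit 4 is attached to the pregnancy test, haematology and chemistry, PK and vital signs. It is not attached to pen return, diary review or the success assessment. Section 4.1 sets the condition for the observed dose: "The second in clinic administration (Visit 4) will not include any onsite training or support, other than the IFU, which could assist the subject". The synopsis says much the same, and Section 6.8.1 adds that this dose is given with no further training.

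**The concern.** The primary endpoint is meant to show whether people can use the pen eight weeks after training with nothing but the IFU to help them. A failed home dose may first come to light at Visit 4, because that is when the pen comes back and home success is judged. If staff then ask what went wrong, or go through the missed steps, and the observed dose follows, the subject or caregiver has just been reminded of the steps about to be scored. Those most likely to be reminded are those who erred at home, so the Week 8 success rate would be pushed upwards.

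Footnote d makes the silence look more like an oversight: the protocol fixes an order relative to dosing for several procedures, but not for these. A compliance query is also a required procedure, so a site might not think of it as training or support. Dose time is recorded, but nothing says that the time of the query is, so the order might not be recoverable afterwards.

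**Working it through.** **1. What a compliant site may do before the dose.** Setting Sections 6.8.2 and 4.1 side by side: the first requires a query some time during Visit 4; the second excludes help at the Visit 4 injection other than the IFU. The closing clause of the Section 4.1 sentence, about assisting the subject, can be read as describing the excluded help or the IFU. On the first reading, anything that could help is excluded; on the second, all on-site training and support is excluded. Either way, a pre-dose conversation that teaches technique breaches the plan. What remains open is a query that does not obviously help, which is the kind least able to move the endpoint.

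**2. What the documents say the contact consists of.** The query concerns compliance and sits under Section 6.8, whose subject is treatment compliance. Its content is not given. The root-cause work is described as scripted and recorded on an error/failure form; no interview with the subject is mentioned. Details of the form and the Observer Checklist are in the Study Reference Manual, which is not among the documents and may set the running order.

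**3. Precision of the primary estimate.** Protocol Section 9.2.2 tabulates exact 95% intervals, and all 22 reproduce to rounding with Clopper-Pearson limits. At an observed 92%:

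- N = 100 (92/100): 84.84 to 96.48 (table: 85, 96); half-width (96.48 − 84.84)/2 = 5.8 points.
- N = 50 (46/50): 80.77 to 97.78 (table: 81, 98); half-width (97.78 − 80.77)/2 = 8.5 points.

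One failure turned into a success moves the rate by 1/100 = 1 point or 1/50 = 2 points.

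**4. Possible shift.** The documents give none of the inputs, so every value here is an assumption:

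shift = h × r × q × a

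where h is the share of subjects with a use failure at home, r the probability that such a subject would fail again at Week 8 with the IFU and no cue, q the share queried before the dose, and a the share of those repeat failures that the query averts.

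| Case | h | r | q | a | Shift (points) |
|---|---|---|---|---|---|
| Low | 0.02 | 0.10 | 0.25 | 0.25 | 0.0125 |
| Middle | 0.05 | 0.25 | 0.50 | 0.50 | 0.31 |
| High | 0.10 | 0.40 | 1.00 | 0.75 | 3.0 |

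If only subjects who failed at home are cued, the shift cannot exceed h, that is 2 to 10 points over this range of h. Reaching that ceiling would require every home failure to recur at Week 8 without a cue, every such subject to be queried first, and every query to work.

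**5. What depends on the estimate.** Protocol Section 9.1 and SAP Section 2.4 plan no hypothesis test and no comparison of the two labels. No success threshold is set. Fixing the order would leave the sample size and the precision table unchanged.

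**The case for a change.** The strongest case for a change is that it costs two sentences. The discussion of the home dose could move into the one-hour observation period that Section 6.8.1 already requires after the Visit 4 injection, with no extra visit, staff or data. The no-help rule limits what staff may offer; it does not schedule a required query, so sites may differ in good faith. All subjects at a site share one label format and each label is reported separately, so local habits could affect one estimate more than the other. In the high case, 3.0 points is about half of the 5.8-point half-width.

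It stands that the order is not printed, that practice could vary between sites, and that any cueing would be favourable to the device. The rest weighs less. The change also has a cost: asking about the Week 4 injection only after another has been performed may blur recall of it. That recall may feed the compliance assessment and the root-cause analysis of failed injections, which Section 3 lists as an endpoint. A strict rule would also be awkward where staff must ask what happened in order to decide whether a pen fault is a reportable device incident. Finally, the plan openly allows other reminders: the IFU may be consulted during the injection (the in-clinic checklist shell in SAP Appendix 9), the home checklist takes its user through the steps, and Section 6.8.2 lets subjects ask for further training or assistance, with the need documented. Ordering the query would leave all of these in place.

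**Conclusion.** The observation is accurate but calls for no change. This is a gap in running order that a site fills sensibly by applying the restriction on help at Visit 4, and the Study Reference Manual may already fill it. No bias in the primary endpoint is shown: that the query covers technique, and that root-cause work involves questioning the subject before the dose, are both inferences. The illustrative shift is about 0.3 point in the middle case and 3.0 in the high case, each below the half-widths of 5.8 and 8.5 points at an observed 92%, in a study with no decision threshold. Those shifts rest on four assumed inputs and on cueing being confined to subjects who failed at home. Fixing the order would exchange a small, unproven risk of cueing for a possible loss of recall about the home dose. The sponsor could confirm to sites that the restriction covers all contact before the Visit 4 dose, but this is optional and the analysis does not depend on it.

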# 6.9. Treatment of Study Treatment Overdose

The dose of mepolizumab considered to be an overdose has not been defined. There are no known antidotes and GSK does not recommend a specific treatment in the event of a suspected overdose. The investigator will use clinical judgment in treating the symptoms of a suspected overdose.

# 6.10. Treatment after the End of the Study

The investigator is responsible for ensuring that consideration has been given to the poststudy care of the subject's medical condition, whether or not GSK is providing specific post-study treatment.

There are no plans to provide mepolizumab following study completion.

## 6.11. Concomitant Medications and Non-Drug Therapies

#### 6.11.1. Permitted Medications and Non-Drug Therapies

Throughout the study, subjects are to be maintained on their baseline standard of care asthma treatment.

**For subjects previously receiving mepolizumab**, additional asthma medications such as theophyllines or anti-leukotrienes will be permitted provided that they have been taken regularly in the 3 months prior to first dose of mepolizumab treatment (Visit 2, Week 0).

**For subjects who have not previously received mepolizumab,** subjects must have a well-documented requirement for regular treatment with high dose inhaled corticosteroid (ICS) in the 12 months prior to Visit 1 with or without maintenance oral corticosteroids (OCS).

- Subjects  $\geq 18$  years old:
  - ICS dose must be ≥880 mcg/day fluticasone propionate (FP) (exactuator) or equivalent daily.
  - For ICS/LABA combination preparations, the highest strength approved maintenance dose in the local country will meet this ICS criterion.
- Subjects  $\geq 12$  to  $\leq 17$  years old:
  - ICS dose must be  $\geq$ 440 mcg/day FP (ex-actuator) or equivalent daily.
  - For ICS/LABA combination preparations, the mid-strength approved maintenance dose in the local country will meet this ICS criterion.

(Subjects will be permitted to be enrolled without continuous high dose ICS providing the subject was receiving continuous ICS and the Investigator attests that the subject should have been treated with high dose ICS to mitigate the risk of exacerbations but financial or tolerance issues prevented the use of high-dose ICS. Such subjects should be discussed with GSK Medical Monitor prior to enrolment)

Subject not previously receiving mepolizumab must also be receiving current treatment with an additional controller medication, besides ICS, for at least 3 months or a documented failure in the past 12 months of an additional controller medication [e.g., LABA, LTRA, or theophylline] for at least 3 successive months.

All concomitant medications taken during the study will be recorded in the eCRF. In addition, all medications taken by the patient for the treatment of asthma including asthma exacerbations in the 12 months prior to Visit 1 must also be recorded in the eCRF. The minimum requirement is that the drug name and the dates of administration are recorded.

